Assessment Training and Monitoring of Treatment Integrity. Assessments will be completed by a trained, supervised, advanced (i.e., BA or higher) evaluator who will be kept blind to participant’s group assignment. The evaluator will initially be trained to an inter-rater reliability of ≥ 0.80 . Assessments will be audio recorded and will be checked periodically to minimize rater drift. To Date most recently revised (02/16/18)

ensure fidelity to the intervention and consistency between therapists, study therapists will undergo training in this approach including directed readings and regular supervision of on-going cases. Treatment sessions will be audio recorded and a randomly selected 15% of sessions will be reviewed to ensure adherence to the treatment protocol.

Participant Withdrawal. Participants may be withdrawn from the study for any of the following reasons: 1) A significantly deteriorating clinical course, such as the emergence of active suicidal ideation or a need for hospitalization, 2) Significant adverse reaction to tDCS, assessed using a modified version of the Systematic Assessment for Treatment Emergent Events (SAFTEE), 3) Serious physical illness, 4) Missing two consecutive study visits, 5) Initiation or reinstitution of other treatment (psychosocial treatment with proven efficacy, psychotropic medication changes) during the acute treatment phase, 6) Investigators' decision that withdrawal from the study is in the participant's best interest, 7) Participant's decision to withdraw. Reasons for withdrawal will be documented, participants will be referred for appropriate treatment, and we will make every attempt to conduct scheduled follow-ups with those who withdraw. The current study will employ several measures to minimize attrition, including frequent contact with participants for the duration of the study and compensation for participants' time for post-treatment and follow-up assessment visits.

4. Data Analysis

Original Data Analysis Plan:

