For this study we will recruit 32 outpatients with a primary diagnosis of OCD: *Inclusion criteria are as follows:* (1) current DSM-5 OCD diagnosis and current Y-BOCS total score of ≥ 16 , (2) 18-65 years of age; (3) ability to speak, read, write, and understand English sufficiently well to complete study procedures and provide informed consent; (4) no use of psychiatric medications or stable psychiatric medication use for a minimum of 6 week prior to study entry. Psychiatric medications will be limited to the following: serotonin reuptake inhibitors (SRI; including clomipramine), combination antidepressants (including bupropion and SNRIs), buspirone, benzodiazepines, stimulants and/or antipsychotics (with the exception of aripiprazole); (5) naive to tDCS; *Exclusion criteria include:* (1) active substance use disorder; (2) lifetime diagnosis of psychotic or bipolar mood disorder; (3) previous minimally adequate trial of ERP (at least 16 sessions including both therapist and self-directed exposure and response prevention), (4) therapy outside the study protocol which has evidence for efficacy with OCD during the study intervention period, (5) active suicidal or homicidal ideation; (6) organic brain disease or injury; (7) any health problems that would interfere with study participation, including contraindications to tDCS (e.g., skin condition, mental implant in skull), (8) Women who are pregnant or breastfeeding. All women participants of child-bearing age are required to have a negative pregnancy test prior to treatment, and must use medically acceptable birth control during study participation. Medically acceptable birth control includes: established oral, injected, implanted, or vaginal ring hormonal contraception, an intrauterine device (IUD), two barrier contraception methods (condom or occlusive cap with spermicidal foam/gel/film/cream/suppository), or having a vasectomized partner, (10) use of anticonvulsant medications (including depakote, gabapentin, tegretol, dilantin, lamictal) and/or glutamate-acting agents (including n-acetylcysteine, riluzole, amantadine, memantine).

B. Recruitment and Consent Procedures

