
Date most recently revised (02/16/18)

tolerate the discomfort during the sessions but that they can stop the exercises at any time. In the case of a participant who experiences extreme distress, clinical judgment and consultation will be used to determine whether the participant should be discontinued from the study. Participants who experience a significant worsening of symptoms during the study will be discontinued and referred for alternative treatment.

To minimize risk of clinical deterioration, we have excluded participants from entry into the study who have active suicidal or homicidal ideation. At baseline, participants will be provided with a set of emergency contact numbers, including phone numbers for local mental health care providers ([Hospital Names]). One of the PIs or a covering clinician will also be available at all times to study participants in the event of a clinical emergency. All participants will be given oral and written information on how to reach the PIs in the case of such an emergency; participants will be told to contact research personnel by telephone or pager for any significant worsening of symptoms or adverse events, and may be seen for an additional evaluation, which will not be considered a protocol violation. We will assess suicide risk at baseline and every week using item 9 on the BDI-II to screen for suicidal ideation. Any presence (BDI-II item 9 > 0) or increase in suicidal ideation will result in a clinical assessment for suicide risk by the clinician and clinically appropriate steps will be taken (e.g., creating a plan for safety or higher level of clinical care, if necessary). We will monitor clinical symptoms weekly using the BDI, BAI, and Y-BOCS. In the event that a participant experiences significant symptom worsening (i.e., 25% increase of pre-randomization Y-BOCS), he or she will be more thoroughly evaluated and we will take appropriate safety measures such as study withdrawal or a higher level of clinical care, if necessary. Participants will be offered referrals to alternative treatment at study discontinuation.

D.2. Measures to ensure confidentiality

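### The 25% Y-BOCS worsening trigger cannot be reached from a baseline above 80% of the scale maximum, so the only numeric prompt for OCD worsening is lost there

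*Combined protocol and SAP*

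**What the plan says.** Section III.D.1 (Measures to minimize potential risks) sets the monitoring: "We will monitor clinical symptoms weekly using the BDI, BAI, and Y-BOCS". It then gives one numeric rule for OCD severity, a fuller evaluation and safety measures as needed when there is "significant symptom worsening (i.e., 25% increase of pre-randomization Y-BOCS". The rule is introduced with *i.e.*, so it reads as a definition and not as an example.

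The entry criterion in Section III.A is "current DSM-5 OCD diagnosis and current Y-BOCS total score of ≥ 16". Neither the inclusion nor the exclusion criteria cap severity, and Section II.C.1 gives the same floor without a ceiling.

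Other provisions bear on a participant who gets worse:

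- Section III.D.1 also says: "Participants who experience a significant worsening of symptoms during the study will be discontinued and referred for alternative treatment". That sentence carries no score.
- For severe discomfort with the exercises: "In the case of a participant who experiences extreme distress, clinical judgment and consultation will be used to determine" whether the participant stays in the study.
- On participant report: "participants will be told to contact research personnel by telephone or pager for any significant worsening of symptoms or adverse events". On cover: "One of the PIs or a covering clinician will also be available at all times to study participants".
- A severe SAFTEE-SI item, or marked interference from side effects, goes to a physician at once. Any positive answer to BDI-II item 9 leads to a suicide-risk assessment (both Section III.D.1).
- Section II.C.3 (Participant Withdrawal) lists "A significantly deteriorating clinical course, such as the emergence of active suicidal ideation or a need for hospitalization" and also allows withdrawal on the investigators' decision.
- Section III.D.3 sets up a DSMB that reviews safety.

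**The concern.** The trigger is a proportion of the participant's own baseline, but the scale has a top. The higher the baseline, the more points the rule asks for and the fewer points are left. Beyond some baseline the required score lies off the scale. Because entry severity is not capped, participants in that range may enrol.

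For them the weekly Y-BOCS is still collected, but no value of it can start the fuller evaluation. The plan chose to add a numeric prompt to clinical judgment, and that prompt stops working for the most severe participants. This has some practical weight in a treatment that provokes anxiety on purpose and encourages participants to tolerate it, because a score-based prompt does not depend on the therapist's or the participant's impression of whether the distress is expected.

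**Working it through.** **Inputs.** Trigger: 25% above the pre-randomization score (Section III.D.1). Lowest admissible baseline: 16, no upper limit (Section III.A). Scale maximum *M*: not stated in the documents, so 40 is taken as an assumption and 30 to 50 is shown as a range. Scores are taken to be whole numbers. The 25% is stated and not derived, so there is no calculation in the plan to reproduce.

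**Condition.** From baseline *b* the trigger needs a score of at least 1.25 × *b*. That score exists only if 1.25 × *b* ≤ *M*, that is, *b* ≤ 0.80 × *M*. This holds for any *M*.

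**With *M* = 40 (assumed).**

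| Baseline | 1.25 × baseline | Rise needed (whole points) | Room left | Reachable? |
|---|---|---|---|---|
| 16 | 20 | +4 | 24 | yes |
| 24 | 30 | +6 | 16 | yes |
| 28 | 35 | +7 | 12 | yes |
| 32 | 40 | +8 | 8 | just |
| 33 | 41.25 | +9 | 7 | no |
| 36 | 45 | +9 | 4 | no |
| 38 | 47.5 | +10 | 2 | no |
| 40 | 50 | +10 | 0 | no |

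**Sensitivity to the assumed maximum.** First unreachable baseline, the smallest whole number above 0.80 × *M*:

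| *M* | 0.80 × *M* | First unreachable baseline |
|---|---|---|
| 30 | 24.0 | 25 |
| 36 | 28.8 | 29 |
| 40 | 32.0 | 33 |
| 44 | 35.2 | 36 |
| 48 | 38.4 | 39 |
| 50 | 40.0 | 41 |

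If the rule means strictly more than 25%, the cut-off at *M* = 40 moves from 33 to 32.

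**Is there another numeric rule for OCD worsening?** The BDI and BAI totals are collected but given no cut-off. BDI-II item 9 measures suicidal ideation, and the SAFTEE-SI measures side effects. The withdrawal criteria, the extreme-distress provision and participant contact carry no score. For the discontinuation sentence there are two readings. If it takes over the 25% definition, it has the same ceiling; if it does not, it has no number.

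**The case against.** The strongest reply is that the gap is small and well covered. Ratings on the SAFTEE-SI bring in a physician who can withdraw the participant or refer for more intensive care, which is nearly the same consequence as the Y-BOCS trigger. BDI-II item 9 forces a clinical assessment. Therapists see participants twice a week, investigators can withdraw anyone, and a DSMB with OCD expertise oversees safety. The documents give no baseline distribution, so nobody may be in the affected range. The revised analysis plan in Section II.C.4 reports a final sample smaller than expected, so enrolment appears to be over.

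Most of this stands, and it limits the weight of the point. It does not remove the ceiling, because none of those routes gives a number for OCD worsening.

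Three stronger readings are tempting and are not supported:

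- *Very severe participants have no score-based protection.* Not so. SAFTEE-SI ratings and BDI-II item 9 work at every baseline. Only the Y-BOCS prompt is lost.
- *The rule is wrong at lower baselines too, because it asks for +4 at 16 but +8 at 32.* Any relative threshold behaves this way. The documents give no ground for preferring equal absolute points, so this is a design preference and not a defect.
- *The efficacy results are compromised.* No planned analysis uses the trigger.

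**Conclusion.** The point holds as a minor defect in a safety rule. Above 80% of the scale maximum the 25% trigger cannot fire, whatever the maximum is. The specific cut-off of 33 rests on an assumed maximum of 40, on whole-number scores, and on reading the rule as at least 25%.

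What is lost is one automatic prompt. In that range, recognition of OCD worsening as such rests on clinician judgment or participant report. The number of participants concerned cannot be worked out from the documents and may be zero.

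**What to change.** Change the trigger sentence in Section III.D.1 only where it fails. Suggested wording: *Significant worsening is a Y-BOCS at least 25% above the pre-randomization score. Where that value would exceed the scale maximum, it is instead a rise of k points or reaching the maximum, whichever comes first, or worsening judged by the clinician at the weekly assessment. For a participant who starts at the maximum, clinician judgment applies.* The investigators and the DSMB set *k*. Baselines at or below 80% of the maximum are unchanged.

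Illustration with *M* = 40 (assumed) and *k* = 5, a value chosen only as an example:

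- Baselines 33 to 35 need +5 (35 + 5 = 40).
- Baselines 36, 37, 38 and 39 need +4, +3, +2 and +1, by reaching 40.
- Baseline 40 relies on judgment.

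This leaves a step from +8 at 32 to +5 at 33. With *k* at 7 or more, the rule becomes simply reaching the maximum, and the step shrinks to +8 then +7 (33 + 7 = 40). Capping the rise at 5 points for all baselines would also remove the step, but it would bring the trigger forward by 1 to 3 points at baselines 21 to 32, where the present rule works. The defect does not require that.

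The cost is one sentence, using scores already collected. The downside is a few extra evaluations among the most severe participants, some set off by changes of a point or two near the maximum. Raters are trained to an inter-rater reliability of at least 0.80 (Section II.C.3), so some of those changes may be rating error. Since enrolment appears complete, the gain may lie mainly in any reuse of the text.
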